17 ADVERSE EVENTS, ADVERSE DEVICE EFFECTS AND DEVICE DEFICIENCIES

The definitions and procedures for reporting Adverse Events (AE), Adverse Device Effects (ADE), Serious Adverse Events (SAE), Serious Adverse Device Effects (SADE), and Unanticipated Serious Adverse Device Effects (USADE) are presented in the subsections below. It is outmost importance that all staff involved in the investigation is familiar with the definitions and procedures and it is the responsibility for the PI to ensure this.

17.1 Definitions

Adverse Event (AE)

Any untoward medical occurrence, unintended disease or injury or any untoward clinical signs (including an abnormal laboratory finding) in subjects, users or other persons whether or not related to the investigational medical device.

Note 1: This definition includes events related to the investigational device or the comparator. Note 2: This definition includes events related to the procedure involved.

Note 3: For users or other persons, this definition is restricted to events related to investigational medical devices.

Adverse Device Effect (ADE)

Adverse event related to the use of an investigational medical device.

Note 1: This includes any adverse event resulting from insufficiencies or inadequacies in the instructions of use, the development, the implantation, the installation, the operation, or any malfunction of the investigational medical device.

Note 2: This includes any event that is a result of a use error or intentional abnormal use of the investigational medical device.

Device Deficiency (DD)

Inadequacy of an investigational medical device related to its identity, quality, durability, reliability, safety or performance. This may include malfunctions, use error, or inadequacy in the information supplied by the manufacturer.

Serious Adverse Event (SAE)

Adverse event that:

- a) Led to a death, injury or permanent impairment to a body structure or a body function.
- b) Let to a serious deterioration in health of the subject, that either resulted in:
 - A life-threatening illness or injury, or
 - A permanent impairment of a body structure or a body function, or
 - In-patient hospitalization or prolongation of existing hospitalization, or
 - In medical or surgical intervention to prevent life-threatening illness.
- c) Led to foetal distress, foetal death or congenital abnormality or birth defect.

Note: Planned hospitalization for pre-existing condition, or a procedure required by the CIP, without a serious detoration in health, is not considered a serious adverse event.

Serious Adverse Device Effect (SADE)

Adverse device effect that has resulted in any of the consequences characteristic of a serious adverse event.

Unanticipated Serious Adverse Device Effect (USADE)

Serious adverse device effect which by its nature, incidence, severity or outcome has not been identified in the current version of the risk analysis report.

Note: Anticipated SADE (ASADE): an effect which by its nature, incidence, severity or outcome has been previously identified in the risk analysis report.

17.2 Methods for discovering and documenting AE/ADE

All subjects will be carefully monitored for the occurrence of AEs throughout the clinical investigation, from the first day to the completion of follow up. Events prior to randomization will be considered medical history. The PI will collect safety information using non-leading questions such as "Have you experienced any new health problems or worsening of existing conditions?". Events directly observed or spontaneously volunteered by subjects will also be recorded throughout the clinical investigation.

Clearly related signs, symptoms and abnormal diagnostic procedure results should be grouped together and reported as single diagnosis or syndrome, whenever possible.

All AEs, including but not limited to events reported by the subject or reported in response to an open question by the PI or member of the investigation team, which fall into any of the previously defined definitions must be recorded as an AE in the CRF and should include the following information:

- Brief description of the event (diagnosis)
- Date of event onsent (and time, if relevant)
- Date of event resolution (and time, if relevant)
- Severity
- Seriousness
- Causality assessment (i.e. relationship to medical device and/or procedure)
- Event treatment
- Event outcome

Any AE that is ongoing when the subject is withdrawn from the investigation should be followed up until the AE is resolved or the PI decides that the AE is stable and no further follow up is needed.

If the AE meets seriousness criteria it should be subject to expedited reporting as described in *section 18.4*.

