7.2 Anticipated risks with the device

Complications that may occur include:

- Allergic response
- Infection

-

- Dehiscence requiring intervention
- Post-operative edema that may cause shearing or blistering
- Wound site pain/discomfort
- Skin stripping upon removal
- Hypo/hyperpigmentation upon removal
 - Excessive scarring including:
 - o Step off
 - o Contour irregularities
 - o Excessive distortion
 - Poor cosmetic appearance

Previous evaluations have not shown any additional risks in comparison to those associated with existing wound closure methods [6]. Any adverse event, related as well as un-related to the device, will be reported in the CRF during this investigation and included in the Safety Analysis.

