9.6.4 Methods of Assigning Subjects to the different treatment arms

When the subjects are consented into the investigation they are given a unique three-digit identification number. If the subject is found eligible he/she will be allocated to the next available randomization number, a code of two digits, and the corresponding randomization envelope opened. The envelope contains information on group allocation in accordance with the randomization list. This is not a blinded investigation and both the Investigator and subject will be aware of the group allocation after randomization. The subject's identification number and randomization number will be noted in applicable investigation logs, Case Report Form (CRF) and in the medical journal system for each subject

Subject withdrawal or discontinuation

Subjects and/or legal representatives are free to discontinue participation in the clinical investigation at any time and are not required to give a reason for their decision. However, they that wish to discontinue the investigation should always be asked about the reason(s) for discontinuation and about the presence of any adverse events/adverse device effects and, if possible, be assessed by an Investigator. Discontinuation from the clinical investigation will not affect the future treatment/care of the subject.

If the subject and/or legal representative(s) will withdraw the consent no further data will thereafter be recorded. Data collected up to the date of window and informed consent will be used in the data analysis and for the Clinical Investigation Report (CIR).

Subjects may be withdrawn from the clinical investigation at any time, if deemed necessary by the PI.

Specific reasons for withdrawal of subjects from this clinical investigation are:

- The decision of a subject and/or legal representative(s) to withdraw from the clinical investigation (including if the subject withdraws informed consent).
- The PI deems the subject is unfit for the investigation or suspects' poor CIP compliance.
- Subject is lost to follow-up.

In case of withdrawal, all AEs/ADEs should be followed up. Any questionnaires should be returned by the subject.

In case of subjects lost to follow up; at least 3 documented attempts to reach the subject shall be made prior to categorizing the subject as "lost to follow-up".

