9.8 Clinical Investigation Procedures

9.8.1 Schedule of clinical investigation procedures/assessments

The assessments and procedures that will be performed during the clinical investigation are illustrated in *Table 3* below.

Study assessment	Visit 1 Day 0	follow-up 1 Day 10 (+/- 2 days)	follow-up 2 Day 30 (+/- 2 days)
Study information	Х		

Informed consent	Х		
Demographics	Х		
Relevant Medical and Surgical history	Х		
Physical examination (Type, size, location of laceration)	Х		
Inclusion/Exclusion criteria	Х		
Randomization	Х		
Wound preparation, e.g. cleansing ¹	Х		
Local Anesthesia and/or Sedation ²	Х		
Device application ³	Х		
Dressing application	Х		
Study participant instructions ⁴	Х		
Device and dressing removal ⁵		X	
Photographs taken ⁶	Х	X	Х
Visual Analog Scale (VAS)	Х	X	
Wound healing satisfaction questionnaire			X
Subject interview		Х	Х
Adverse event	Х	Х	Х
Medical review / Concomitant medication	Х	Х	Х
Study Exit			Х

¹ According to clinical routine.

² According to clinical routine. Zip group: Anesthesia and/or sedation only use if deemed necessary by Investigator. Document in Concomitant Medication Log.

³ Test group will be treated with Zip 4 device and SoC group with conventional sutures as wound closure.

⁴ Instructions prior discharge regarding post-treatment and additional follow up visits.

⁵ suture ir device removal will be conducted at FU session 1 at the PED or at home by a member of staff of the study

⁶ Photographs will be taken at the wound area during Visit 1 and follow up visits by the site personnel, . Please be aware of not adding any personal numbers or identifying characteristics on the photographs, only subject identification number and visit information.

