9.8.1.2 Follow up 1 (Day 10 +/- 2 days)

At the first follow up the device, either Zip 4 device or SoC sutures will removed at day 10(+-2 days). Prior discharge at visit 1 the subjects will receive instructions that if:

- 1) Treated with Zip 4 device the subject and their legal representative(s) will remove the subject themselves at day 10. If necessary, the subject/legal representative(s) may call the A&E for assistance during the removal.
- 2) Treated with SoC sutures the subject and their legal representative(s) will visit the Pediatric Emergency Department or at home for removal of the sutures. During the follow up after device removal the subject will be asked about any adverse events that may have occurred, and a review of the concomitant medication. The subject will be interviewed about the usage of the device, and will fill out the questionnaire, VAS, and photograph the laceration. Next follow up day 30 will be scheduled if not done at visit 1.

All of the above can be done in assistance by the legal representative(s), if needed.

The following assessments/procedures will be performed at follow up 1:

- Subject interview
- VAS
- Cosmetic Outcome
 - High definition photos will be taken of the laceration
 - Registration of any Adverse Events
- Registration of Concomitant Medication

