Has the subject experienced any Adverse Events/Adverse Device Effects during the treatment procedure? If YES , please fill out the Adverse Event/Adverse Device Effect Log.	🗌 NO 🔄 YES	
Has any device deficiency been detected? If YES , please fill out the Device Deficiency Form.	🗌 NO 🔄 YES	
FOLLOW UP CALLS SCHEDULED		
Follow-up 1 (10 days +/- 2 days) scheduled? (Home/PED)	🗌 NO 🔄 YES	
Follow-up 2 (30 days +/- 2 days) scheduled?(Home/ PED)	🗌 NO 🔄 YES	

Date (DD-MMM-YYYY): _____ Investigator signature:

					12/1/18	גרסה 1 מתאריך
ZipLine	Case Report Form				_ - _ Subject ID No No	 Randomization
	FOLLOW (U P 1 (10 D A	AYS -	+/- 2 DAYS)		
Date (DD-M	MMM-20YY) and Time (HH:MM)	-		- 2 0		:
DEVICE REMO	VAL					
Has the device l period?	been properly attached during	the healing	□ NO □ YES			
If NO , please pro	ovide a reason:					
Date (DD-MMM device removal:	1-20YY) and Time (HH:MM) of	, _ _ -		_ -  2 0 _ _	_ _ : _ _	.
Device removed as scheduled (10 days $\pm/-2$		🗆 NO	D YES			
If NO , please pro	ovide a reason:					
Adhesive remov removal? (ONL) GROUP)	Ver used for Zip	NO [] Y	ES	🗌 N/A		
INTERVIEW						
If the subject would need laceration repair again, would the subject prefer the treatment he/she received in this study?		🗌 I do not know	N			
How satisfied is the subject with the removal procedure?		procedure?	□ Sa □ N □ Sa	ery satisfied atisfied leither satisfied omewhat satisf ery dissatisfied		
Any additional comments the subject would like to inform about the treatment he/she received:						

CONCOMITANT MEDICATION QUESTION		
Has there been any new or changes to the concomitant medication since last time?	□ NO	
If YES , please fill out the Concomitant Medication Log.	YES	

YES

🗌 NO

interview questions?

Has the legal representative(s) helped out to answer the

_____ - _____ Subjec No

ect ID No	Randomization

ADVERSE EVENT/ADVERSE DEVICE EFFECT QUESTION		
Has the subject experienced any Adverse Events/Adverse Device Effects since last time?	🗌 NO	
If YES , please fill out the Adverse Event/Adverse Device Effect Log.	YES	
Has any device deficiency been detected?	□ NO	
If YES , please fill out the Device Deficiency Form.	YES	

VAS – FOLLOW UP 1		
Has the subject/legal representative(s) completed the VAS form ?	□ NO □ YES	
	VAS Score	
If NO , please provide a reason:		

PHOTOGRAPHING - FOLLOW UP 1	
photographs on the laceration?	□ NO □ YES
If NO , please provide a reason:	

FOLLOW UP SCHEDULED		

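### Follow-up CRF pages do not prompt for several of the local complications listed in section 7.2, so the between-arm safety comparison risks incomplete and possibly unequal recording

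*Protocol*

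**What the plan says.** **Endpoint.** Protocol section 9.4 makes the incidence and severity of adverse events in both arms a secondary safety endpoint. Section 9.8.4 says anticipated and unanticipated events will be recorded and compared between the groups.

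**What is anticipated.** Section 7.2 lists local complications, among them "Dehiscence requiring intervention", allergic response, infection, edema with shearing or blistering, skin stripping, pigment change and excessive scarring.

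**How events are found.** Section 17.2: "The PI will collect safety information using non-leading questions such as" and then one example about new or worsening health problems. It continues: "Events directly observed or spontaneously volunteered by subjects will also be recorded throughout the clinical investigation".

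**What the CRF asks.** Both follow-up pages ask "Has the subject experienced any Adverse Events/Adverse Device Effects since last time", with a no/yes answer leading to the log, and whether a device deficiency was detected. Neither page lists any complication.

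**Who looks at the wound.** In Table 3 (section 9.8.1) the row that begins "Physical examination (Type, size, location of laceration" is marked for day 0 only. Photographs are scheduled at days 0, 10 and 30, and two blinded plastic surgeons score them with the WES (sections 9.1 and 9.8.3.2).

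**Blinding.** Section 9.6.4: "This is not a blinded investigation and both the Investigator and subject will be aware of the group allocation after randomization".

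**Removal at day 10.** Footnote 5 of Table 3 states: "suture ir device removal will be conducted at FU session 1 at the PED or at home by a member of staff of the study". Section 9.8.1.2: "Treated with Zip 4 device the subject and their legal representative(s) will remove the subject themselves at day 10" (evidently meaning the device).

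**The concern.** For a skin-closure device the informative safety events are local and mostly mild. A child of 4, or a parent, may not think of a blister or a patch of stripped skin beside a known wound as a new health problem. Section 17.2.1 counts asymptomatic findings and purely clinical observations as mild events. Questions cannot elicit those; someone has to look and then write them down, and no follow-up page reminds staff to do so.

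Two things are at stake. A small arm can look free of complications because the events were not recorded. And if one arm is looked at more closely than the other, a difference can appear or vanish for that reason alone. The plan relies on this channel: section 17.5 appoints no data monitoring committee and rests early detection of risk on adverse-event reporting and monitoring.

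**Working it through.** **1. What follow-up covers.** Section 7.2 complications against the follow-up instruments:

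| Section 7.2 item | Dedicated follow-up item |
|---|---|
| Step-off, contour irregularity, poor cosmetic appearance | WES items 1, 2 and 6 (blinded) |
| Excessive scarring | In part: WES item 3, scar width |
| Infection | In part: WES item 5, redness or discharge |
| Wound pain | VAS at day 10; scar-pain line in the day 30 questionnaire |
| Dehiscence requiring intervention | None |
| Blistering or shearing | None |
| Skin stripping on removal | None |
| Allergic response | None |
| Pigment change | None |

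The follow-up 1 page also asks about device attachment, timing of removal and use of adhesive remover. None of these names a complication. The WES serves a performance endpoint (section 9.3), and no text says that a poor WES item becomes an adverse-event entry.

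**2. Whether both arms are seen alike.**

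- Staff remove either closure: section 9.1, Table 3 footnote 5, and the pre-discharge text of section 9.8.1.1.
- Zip families remove the device themselves, while suture subjects have the sutures removed at the department or at home: section 9.8.1.2.
- Telephone follow-up: the closing list of section 9.8.1.1, and section 9.8.1.3.

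Under the second reading, skin stripping could occur in the Zip arm with no staff present, while suture removal would be a visit.

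**3. Size, as illustration only.** The plan states no safety rate and no safety sample size. Its one calculated figure, 12 per group for closure time, reproduces by the two-sided normal approximation: 2 × (1.960 + 1.282)² × (22/30)² = 11.3, rounded up to 12. It does not bear on this point. The total is given as 30 (Synopsis, section 9.1), 60 (section 9.6.3) and at most 26 (section 11.2), so 15 and 30 per arm are both shown.

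Assumptions not found in the documents: true risk p, and share of true events recorded s. With n children in an arm, P(no event recorded) = (1 − p·s)^n.

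| p = 10% | s = 100% | s = 90% | s = 50% |
|---|---|---|---|
| n = 15 | 0.90^15 = 0.21 | 0.91^15 = 0.24 | 0.95^15 = 0.46 |
| n = 30 | 0.90^30 = 0.04 | 0.91^30 = 0.06 | 0.95^30 = 0.21 |

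At p = 5% the chance of an empty arm is already 0.46 (n = 15) or 0.21 (n = 30) with complete recording. It rises to 0.68 or 0.47 when half of events are recorded.

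Unequal recording, with p = 20% in both arms of 30: the true expectation is 30 × 0.20 = 6 events in each arm. With s = 90% in one arm and 50% in the other, the expected counts are 6 × 0.9 = 5.4 and 6 × 0.5 = 3.0.

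**4. What size alone does.** With no event in an arm, the one-sided 95% upper bound on the risk is 1 − 0.05^(1/n): 18.1% at n = 15 and 9.5% at n = 30, even if every event is recorded.

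**The case against.** A reader might infer that adverse events rest on a single open question. They do not: section 17.2 speaks of questions in the plural, gives one as an example, and also requires observed and volunteered events to be recorded. Non-leading questioning is not an error.

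A reader might also infer that nobody checks the wound after day 0. The Table 3 row describes the injury at baseline, and its absence later does not mean the wound goes unseen. By most of the text, staff remove the closure at day 10; section 5.7 says those staff are experienced pediatric emergency physicians. Section 5.8 has the treating physician judge whether wear should be extended because of gapping. Site personnel photograph the wound at both follow-ups, and blinded surgeons score redness, discharge and edge defects. Section 5.7 also requires training in correct reporting of complications.

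Further, the detection rates above are assumed, no text shows unequal probing, and a tick list completed by the same unblinded staff does not blind anyone.

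All of that stands, and it narrows the point. It does not fill the five empty rows of the first table, supply a link from the WES to the adverse-event log, or settle who sees Zip wounds at day 10. Nor is this a matter for an unseen analysis plan: the CRF is appended to the protocol, and data not collected cannot be analysed later.

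**Conclusion.** The point holds as a risk, not as a demonstrated loss. Neither follow-up page prompts for dehiscence, blistering or shearing, skin stripping, allergic response or pigment change, and nothing carries an adverse WES finding into the adverse-event log. In an open-label comparison with contradictory text on day 10 removal, recording of these events may be incomplete and may differ by arm.

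The stronger statement, that these events are under-recorded, is not supported: the documents give neither an event rate nor a detection rate, so the size of any shortfall cannot be derived. The shifts shown (for example from 4% to 21% for an empty arm of 30 at 10% risk) depend on the assumed halving of detection. Much of the chance of an empty arm comes from the small sample itself. The change is worth making because it costs little.

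**What to change.** 1. Keep the open question first. Then add to the follow-up 1 and follow-up 2 CRF pages a short yes/no list of the section 7.2 local complications (infection, dehiscence, blistering or edema, skin stripping, allergic response, pigment change, excessive scarring). Complete it identically in both arms, with severity for each yes.
2. Tabulate these solicited events by arm, separately from spontaneously reported ones.
3. State whether, and how, an adverse WES item leads to an adverse-event entry.
4. Reconcile section 9.1, Table 3 footnote 5 and the staff-removal text of section 9.8.1.1 with section 9.8.1.2 and the telephone wording in sections 9.8.1.1 and 9.8.1.3, so that it is clear who sees the wound at each follow-up in each arm.

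Cost: a tick list on two existing pages, one extra table and a minute or two per contact. No extra visit, reader or procedure is needed. The count of mild events will rise, and the assessor remains unblinded.

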17.2.1 Severity

Severity describes the intensity of an AE and will be assessed as:

- 1. Mild: asymptomatic or mild symptoms; clinical or diagnostic observations only; intervention not indicated.
- 2. Moderate: minimal, local or non-invasive intervention indicated, limiting age-appropriate instrumental activities of daily living.
- 3. Severe or medically significant by not immediately life-threatening: hospitalization or prolongation of hospitalization indicated; disabling; limiting self-care activities of daily living.
- 4. Life-threatening consequences; urgent intervention indicated.
- 5. Death related to AE.

If an AE changes in severity, it should be reported as an AE of new severity but with the same description and identifier.

17.2.2 Causality

Causality is the relationship between the use of medical device (including the investigational device, the comparator and the medical – surgical procedure) and the occurrence of each AE.

During causality assessment activity, clinical judgment shall be used and the relevant documents, such as the CIP, or the risk analysis report, shall be consulted as all the foreseeable SAEs and the potential risks are listed and assessed there. The presence of confounding factors, such as concomitant medication/treatment, the natural history of the underlying disease, other concurrent illness or risk factors shall also be considered.

For harmonizing reports, each SAE will be classified per five different levels of causality. The Sponsor and the Investigator will use the following definitions to assess the relationship of the SAE:

- Not related: relationship to the device or procedures can be excluded when:
 - The event is not a known side effect of the product category the device belongs to or of similar devices and procedures;
 - \circ $\;$ The event has no temporal relationship with the use of the investigational device or the procedure;
 - The serious event does not follow a known response pattern to the medical device (if the response pattern is previously known) and is biologically implausible;
 - The discontinuation of medical device application or the reduction of the levels of activation/exposure when clinically feasible and reintroduction of its use (or increase of the level of activation/exposure), do not impact on the serious event;
 - The event involves a body-site or an organ not expected to be affected by the device or procedure;
 - The serious event can be attributed to another cause (e.g. an underlying or concurrent illness/clinical condition, an effect of another device, drug, treatment or other risk factors);
 - The event does not depend on a false result given by the investigational device used for diagnosis when applicable;
 - Harms to the subject are not clearly due to use error;
 - To establish the non-relatedness, not all the criteria listed above might be met at the same time, depending on the type of device/procedures and the serious event.
- Unlikely: the relationship with the use of the device seems not relevant and/or the event can be reasonably explained by another cause, but additional information may be obtained.
- Possible: the relationship with the use of the investigational device is weak but cannot be ruled out completely. Alternative causes are also possible (e.g. an underlying or concurrent illness/clinical condition or/and an effect of another device, drug or treatment). Cases were relatedness cannot be assessed or no information has been obtained should also be classified as possible.
- Probable: the relationship with the use of the investigational device seems relevant and/or the event cannot reasonably be explained by another cause, but additional information may be obtained.
- Causal relationship: the serious event is associated with the investigational device or with procedures beyond reasonable doubt when:
 - The event is known side effect of the product category the device belongs to or of similar devices and procedures;

- The event has a temporal relationship with investigational device use/application or procedures;
- The event involved a body-site or organ that
 - the investigational device or procedures are applied to;
 - the investigational device or procedures have an effect on.
- The serious event follows a known response pattern to the medical device (if the response pattern is previously known);
- The discontinuation of medical device application (or reduction of the level of activation/exposure) and reintroduction of its use (or increase of activation/exposure), impact on the serious event (when a clinically feasible);
- Other possible causes (e.g. an underlying or concurrent illness/clinical condition or/and an effect of another device, drug or treatment) have been adequately ruled out;
- Harm to the subject is due to error in use;
- The event depends on a false result given by the investigational device used for diagnosis, when applicable;
- To establish the relatedness, not all the criteria listed above might be met at the same time, depending on the type of device/procedures and the serious event.

The Sponsor and PI will distinguish between the AEs related to the investigational device, the standard of care and those related to any procedure specific to the clinical investigation. An AE can be related to both the procedure and the device. Complications of procedure are considered not related if the said procedure would have been applied to the subjects also in the absence of the device use/application.

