7.1 Anticipated clinical benefits

The potential benefits of the Zip device over standard of care closure include:

- Improved cosmetic outcome
- Greater patient satisfaction
- No skin piercing
- Reduced procedure time
- Rapid one-person closure time
- Eliminate need for skin sutures
- Improved staff safety reduced needle stick

The investigation is intended to measure the result of some or all of these benefits.

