9.4 Secondary endpoints (safety)

The incidence and severity of adverse events associated with the Zip 4 Surgical Skin Closure Device and Standard of Care closure sutures.

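### The causality rule in section 17.2.2, read literally, classes complications of suturing as 'not related' while Zip complications stay gradable, which contradicts the comparator's place in causality and in the safety endpoint

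*Protocol*

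**What the plan says.** The safety endpoint in section 9.4, repeated in the synopsis, is "The incidence and severity of adverse events associated with the Zip 4 Surgical Skin Closure Device and Standard of Care closure sutures".

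Section 17.2.2 sets out how events are attributed. It defines causality as the link between use of a medical device and an event, with this scope: "including the investigational device, the comparator and the medical – surgical procedure) and the occurrence of each AE". Near its end it says that the sponsor and the principal investigator "will distinguish between the AEs related to the investigational device, the standard of care and those related to any procedure specific to the clinical investigation". Two sentences later the paragraph closes with the exclusion, that complications of a procedure "are considered not related if the said procedure would have been applied to the subjects also in the absence of the device use/application".

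The section also defines five causality levels, set for serious adverse events. 'Possible' applies where "the relationship with the use of the investigational device is weak but cannot be ruled out completely". 'Probable' likewise names only the investigational device. 'Not related' and 'Causal relationship' refer to the device or the procedures.

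**The concern.** An endpoint worded as events associated with each closure method needs a relatedness judgement in both arms, made by the same rule. The exclusion sentence asks what would have happened without the device. If 'the device' is the Zip, the answer for these children is suturing. Its procedural complications, and those of the injection or sedation given for it, then become 'not related' by definition. A complication of applying or removing the Zip cannot be excluded in this way, because that step would not have taken place without the Zip.

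What is at stake is any tabulation limited to related or associated events. Suture-arm events could be under-attributed, so that Zip looks worse than it is. Needles and sedation are also the burdens that sections 6 and 7.1 expect Zip to reduce, and attribution would be least reliable for them.

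**Working it through.** The protocol states no figure on this point, so the check is mainly a reading of the passages against each other.

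**1. Does the exclusion reach suturing?** Inclusion criterion 2 (section 9.6.1) admits only children who need suture closure as standard of care. Section 9.5 calls sutures the current clinical routine. Section 9.8.1.1 gives suture subjects local anaesthesia and/or sedation by clinical routine, and Zip subjects only when the investigator finds it necessary. So suturing with its routine anaesthesia or sedation is what would be done without the Zip, and the literal wording covers it.

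**2. Does it act equally in both arms?** Only in part.

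| Source of complication | Zip arm | Suture arm |
|---|---|---|
| Wound cleaning, dressing | excluded | excluded |
| Anaesthesia or sedation that would have been given anyway | excluded | excluded |
| Closure step and removal | gradable | excluded if classed as procedural |
| Suture material as comparator | not applicable | can still be standard-of-care related |

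The asymmetry comes from the closure step, and from the greater use of anaesthesia and sedation expected with sutures.

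**3. Does the surrounding text agree?** No. The definition of causality includes the comparator and the procedure. Note 1 to the adverse event definition (section 17.1) includes comparator events. The closing paragraph of 17.2.2 asks for a standard-of-care category, then adds the exclusion without exempting it. 'Possible' and 'Probable' give no wording for grading a suture event.

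**4. Can the CRF settle it?** No. The adverse event log scores 'Procedure' and 'Device' separately as unlikely, possibly or likely. It has no comparator field and no 'not related' code.

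**5. Possible size, under assumptions only.** Assume equal true related-event rates in both arms. Section 9.6.3 gives 30 per arm, while the synopsis and section 9.1 give 30 in total (15 per arm), so both are shown. For a events against 0 with n per arm, the two-sided Fisher p is 2 × C(n, a) / C(2n, a).

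- 30 per arm, 10%: 3 v 0; p = 2 × 4,060 / 34,220 = 0.24
- 30 per arm, 20%: 6 v 0; p = 2 × 593,775 / 50,063,860 = 0.024
- 30 per arm, 30%: 9 v 0; p = 0.002
- 15 per arm, counts rounded: 2 v 0, 3 v 0 and 4 v 0; p = 0.48, 0.22 and 0.10

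If about half of the suture-arm events were reclassified, 30 per arm would give 3 v 2, 6 v 3 and 9 v 4 (p = 1.0, 0.47 and 0.21). The spurious difference therefore runs from about 3 percentage points (1/30) to 30 (9/30), depending wholly on the assumed rate and on how sites read the sentence.

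**The case against.** A reader might infer that control-arm harms vanish from the safety comparison, or that the safety data cannot be interpreted. The documents do not support that, for these reasons.

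- **All events are kept.** Section 7.2 puts every adverse event, related or not, into the CRF and the safety analysis. Section 9.8.4 compares adverse event recordings between the groups with no relatedness filter. A suture complication marked 'not related' stays in that comparison.
- **Nothing gives the exclusion sentence precedence.** The standard-of-care category stands in the same paragraph, and no text says that one yields to the other.
- **The protocol sometimes calls sutures a device** (sections 9.5, 9.8.1.1 and 9.8.4). On that usage suturing would not occur without the device, and the exclusion would not touch it.
- **The five levels are set for serious events**, and the CRF log has no code in which the exclusion could be recorded as written.
- **Related information is captured elsewhere.** Anaesthesia and sedation use and the pain VAS are collected in both arms.

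The first, second, fourth and fifth points stand, and they limit the problem to attribution. The third shows an ambiguity but does not resolve it. Within this paragraph the investigational device and the standard of care are listed as separate things, so 'the device' most naturally means the Zip.

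Staff injuries are a separate matter. Note 3 in section 17.1 says "For users or other persons, this definition is restricted to events related to investigational medical devices", so a needle stick while suturing would not count as an adverse event, although section 7.1 lists "Improved staff safety reduced needle stick" among the potential benefits. That section commits the trial to measuring only some or all of these benefits, no endpoint measures staff injury, and the CRF asks only about the subject. It does not carry the main point.

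**Conclusion.** The point holds as an internal contradiction that invites different classification by arm. The literal rule covers procedural complications of suturing and its routine anaesthesia or sedation. The endpoint, the definition of causality and the standard-of-care category all require such events to be attributable. The likely direction is against Zip on associated events. The conclusion rests on reading 'the device' as the Zip, and on 'associated with' in section 9.4 requiring attribution.

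The exposure is confined to analyses restricted to related or associated events. The defective 'Possible' and 'Probable' wording formally affects serious events only. The size cannot be quantified from the documents, and the counts shown are illustrations under assumed rates. The wording should be corrected, but it is no ground for dismissing the safety comparison as a whole.

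**What to change.** 1. In 17.2.2, limit the exclusion sentence to procedures common to both arms, such as wound cleaning and dressing.
2. State one relatedness definition for the allocated closure, Zip or sutures, including its application and removal and any anaesthesia or sedation given for it. Use it for both arms.
3. In 'Possible' and 'Probable', replace the reference to the investigational device with the allocated closure or its procedure.
4. Align the CRF adverse event log by adding a comparator option and a 'not related' level.

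Optionally, extend Note 3 in section 17.1 to the comparator so that staff needle sticks count in both arms. This would also need a CRF prompt for staff events.

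The cost is a wording amendment to 17.2.2 and a small revision of the CRF log. The downside is that a few more events will be classed as related.
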